### ***About the Stroke***

- These questions relate to the Glasgow Coma Scale (GCS) or the Medical Research Council (MRC) Scale
- Able to swallow - *This assessment should be performed in line with local guidelines but, as a minimum, should comprise a bedside assessment*
- Nourishment - *This assessment should be performed in line with local practice but, as a minimum, should include an informal assessment of nutritional status*

### ***Co-enrolment***

Remember you can randomise this patient into another trial if you are uncertain how best to feed them later in this admission (e.g. NG vs PEG, Normal diet vs Normal diet PLUS oral supplements).

FOOD/SER/1/998

## APPENDIX B: Adverse Event Card

Please complete if any patient randomised into FOOD experiences a **major adverse event** (in particular any relating to the allocated feeding policy)

**TO MAINTAIN CONFIDENTIALITY, PLEASE SEND US THIS CARD IN AN ENVELOPE**

Hospital name: \_\_\_\_\_

Patient's family name: \_\_\_\_\_

Given names: \_\_\_\_\_

Date of birth: day \_\_\_\_\_ / month \_\_\_\_\_ / year \_\_\_\_\_

Date adverse event first experienced: day \_\_\_\_\_ / month \_\_\_\_\_ / year \_\_\_\_\_

Details: \_\_\_\_\_

\_\_\_\_\_

*for office use only*

**Please return (in an envelope) to the FOOD Trial Co-ordinating Centre,  
Neurosciences Trials Unit, Western General Hospital, [name]**

**THANK YOU**

for office use only

FOOD/MAC/1/998

## The International Stroke Trials Collaboration (Feed Or Ordinary Diet)

### Hospital Discharge Form

**PLEASE COMPLETE THIS FORM ON THE PATIENT'S DISCHARGE FROM HOSPITAL, TRANSFER FROM THE CENTRE OR DEATH (whichever occurs first) AS ACCURATELY AS POSSIBLE**

**Hospital Details:**

Hospital Number:

or Hospital Name:

**Patient Details:**

Family Name:

Given Name/s:

Date of Birth: day   month   year

Sex: Male  Female

**Affix Patient Sticker Here**

**ABOUT THE STROKE:**

Was stroke diagnosis confirmed in this patient?

YES  NO

If **not** a stroke, please specify the diagnosis:

For office use

**ABOUT THE PATIENT:**

How was the nutritional status assessed before first randomisation (please tick (✓) one or more boxes)

- Informal assessment
- Weight
- Dietitian's assessment
- Anthropometry
- Blood tests
- Other:

For office use

How was the swallowing assessed before the first randomisation (please tick (✓) one or more boxes)

- Bedside assessment (doctor or nurse)
- Bedside assessment (speech & language therapist)
- Videofluoroscopy
- Other:

For office use

**PRIOR to randomisation, did this patient receive:**

Any enteral tube feeds? YES  NO

**SINCE randomisation, has this patient received:** (please tick (✓) one box on each line)

- |   |                              |                             |                                   |
|---|------------------------------|-----------------------------|-----------------------------------|
| Any Parenteral Fluids   | YES  | NO  | If YES complete PARTS 1, 5, 6 & 7 |
| Any feeding via an NG Tube  | YES  | NO  | If YES complete PARTS 2, 5, 6 & 7 |
| Any feeding via another type of tube (e.g. PEG)                               | YES  | NO  | If YES complete PARTS 3, 5, 6 & 7 |
| Any normal hospital diet PLUS supplementary feed                              | YES  | NO  | If YES complete PARTS 4, 5, 6 & 7 |
| Normal hospital diet only   | YES  | NO  | If YES complete PARTS 5, 6 & 7    |
| Other (e.g. total parenteral nutrition), please specify:  |                              |                             |                                   |

For office use

If allocated feeding policy(ies) was(were) **not** followed please give reason(s) below:

For office use

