Supplementation might be achieved by intravenous feeding but in practice this is rarely used or justified in patients with stroke who generally have a gastrointestinal tract which is well able to absorb nutrients. NG tubes are often inserted to allow fluid and food to be given to patients. However, in patients who are unable to swallow, they are not always easy to insert and perhaps because they are uncomfortable they are often pulled out by patients and have to be replaced. This adds to patient distress and interrupts any feeding regime. Furthermore, NG tubes may become displaced and cause aspiration, as well as ulceration of the nostril if use is prolonged. Some workers therefore advocate the increased use of PEG (O'Mahony & McIntyre 1995) which can be performed with little or no sedation and provides an effective and quite acceptable method of enteral feeding. However, PEG is more invasive than NG and has its own complications including aspiration, peritonitis, wound infection and haemorrhage. Indeed there is a low (about 1%), but not insignificant, risk of death related to the procedure (Larson et al 1987, Miller et al 1989, Finucane et al 1991, Pender et al 1993). The published complication rates are low but may not reflect the rates in less specialised centres which do not publish their results (Wanklyn et al 1995). Two randomised comparisons of NG and PEG tube feeding have suggested that the latter provides more effective nutritional support with less interruption of feeding (Park et al 1992, Norton et al 1996). One trial was in patients with severe stroke and showed that those fed by PEG had an implausibly large (70% relative) reduction in case fatality compared with those fed via NG tube (Norton et al 1996). However, this trial only included 30 patients and little data were provided to allow any assessment of the effectiveness of randomisation. It seems most likely that some imbalance in baseline factors accounted for much of the observed difference in outcome. However, despite its limitations, this trial raises important issues about the best way to feed patients with stroke who cannot swallow safely.

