## ***Secondary Outcomes***

---

- Proportion of patients who are dead at one and six months.
- HRQoL amongst survivors.
- Time to hospital discharge.
- Length of stay in hospital which will provide a surrogate outcome for analysis of cost.
- Number of days of tube feeding.
- Adverse effects of feeding regimes.
- Premature cessation of feeding regimes and reasons.

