## PART 2 Fed via a NG Tube SINCE Randomisation (Please enter 99/99/99 or 99 if unknown)

Date first NG tube inserted after randomisation: day   month   year

Number of tubes inserted SINCE randomisation:

Is the NG tube still in situ? YES  NO

If NO, date last NG tube removed: day   month   year

Name(s) of feed given: \_\_\_\_\_

Did NG tube deliver satisfactory volumes of liquid feed? YES  NO  Uncertain

If NG feeding stopped, please indicate the primary reason below (please tick (✓) one box only)

- Patient taking adequate diet and fluids orally
  - Patient discharged/died
  - Difficulties encountered (please specify difficulties below)
  - Other (e.g. feeding futile), please specify: \_\_\_\_\_
- For office use

Were any difficulties experienced? (please tick (✓) one or more boxes)

- No
  - Difficulties with tube insertion
  - Nasal ulceration
  - Other, please specify: \_\_\_\_\_
  - Patient pulled out the tube(s)
  - Aspiration
- For office use

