## PART 3 Fed via another type of tube (e.g. PEG) SINCE Randomisation (Please enter 99/99/99 or 99 if unknown)

Type of tube inserted  Gastric       Duodenal/jejunal

Method of insertion  Endoscopic       Radiological guidance

Date first tube inserted after randomisation: day   month   year

Number of tubes inserted SINCE randomisation:

Is the tube still in situ? YES  NO

If NO, date last tube removed: day   month   year

Name(s) of feed given: \_\_\_\_\_

Did PEG tube deliver satisfactory volumes of liquid feed? YES  NO  Uncertain

If PEG feeding stopped, please indicate the primary reason below (please tick (✓) one box only)

- Patient taking adequate diet and fluids orally
  - Patient discharged/died
  - Difficulties encountered (please specify difficulties below)
  - Other (e.g. feeding futile), please specify: \_\_\_\_\_
- For office use

Were any difficulties experienced? (please tick (✓) one or more boxes)

- No
  - Difficulties with tube insertion
  - Wound infection
  - Haemorrhage from PEG site
  - Other, please specify: \_\_\_\_\_
  - Patient pulled out the tube(s)
  - Aspiration
  - Peritonitis
- For office use

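### The discharge form opens its tube sections only if feed was given, so complications of an attempted insertion without feeding lose their prompted boxes and may be under-recorded

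*Protocol*

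**What the plan says.** The routing table of the Hospital Discharge Form (Protocol, Appendix C) asks what the patient has received since randomisation. A yes to "Any feeding via an NG Tube" sends the site to Part 2. A yes to "Any feeding via another type of tube (e.g. PEG" sends it to Part 3. The heading of Part 3 repeats the condition: "Fed via another type of tube (e.g. PEG) SINCE Randomisation". Part 2 is headed in the same way for NG.

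The prompted list of difficulties lies inside these parts. Both contain "Difficulties with tube insertion" and a box for aspiration. Part 3 alone contains "Haemorrhage from PEG site", wound infection and peritonitis.

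Three other routes do not depend on feed having been given:
- On the routing page, if the allocated policy was not "followed please give reason(s) below" is the instruction, with a free-text line.
- Part 5, for all patients, prompts pneumonia and gastrointestinal haemorrhage. It has write-in lines for other infections and other medical complications, and records in-hospital death with its cause and whether it was thought due to trial treatment.
- The Adverse Event Card (Reporting Major Adverse Events; Appendix B) covers major events in any randomised patient.

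The Secondary Outcomes section lists "Adverse effects of feeding regimes". The Background states that "PEG is more invasive than NG and has its own complications including aspiration, peritonitis, wound infection and haemorrhage".

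**The concern.** Whether a site is prompted for a procedural complication depends on something that happens after randomisation, namely delivery of feed, and the complication itself can prevent that. If a PEG insertion fails, or is complicated before any feed is given, the PEG routing question is truthfully answered no and Part 3 stays blank. If the patient is then fed by NG, the site completes Parts 2, 5, 6 and 7. Part 2 has no box for peritonitis, wound infection or bleeding at the PEG site.

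At stake is a named secondary outcome. The Follow-up section names this form as a source of data on complications of the feeding regime. The Background says that published PEG complication rates are low but may not represent less specialised centres, so a large multicentre trial is well placed to measure them. The section on Duration of Feeding Regimen also intends to use data on how often and why policies were changed; a failed insertion is an obvious reason, yet it has no coded field unless feed was given by that tube.

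**Working it through.** The plan states no figure on this point, so the main check is to trace the form. Take two patients with an attempted PEG, one later fed through it and one not.

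| Event | PEG feed delivered | No PEG feed delivered |
|---|---|---|
| Failed or difficult insertion | Box in Part 3 | Free-text reason for departing from allocation |
| Wound infection | Box in Part 3 | Written in under other infections, Part 5 |
| Peritonitis | Box in Part 3 | Written in, Part 5; card if major |
| Bleeding at PEG site | Box in Part 3 | Written in, Part 5 (its bleeding box is for gastrointestinal haemorrhage); card if major |
| Aspiration at the procedure | Box in Part 3 | Pneumonia box in Part 5 if pneumonia follows; otherwise written in |
| Death in hospital | Part 5, with attribution | Part 5, with attribution |

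The fed patient also has Part 5 and the card. So the same non-fatal event is prompted and coded in one patient and must be volunteered in the other. Deaths are treated identically.

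**Direction.** Suppose a share f of an arm has an attempted insertion but no feed, with complication rate c in those patients. Prompted records lost are then 500·f·c per arm in Trial 3 (1000 ÷ 2 = 500). The difference between arms is 500·(f_PEG·c_PEG − f_NG·c_NG). The protocol gives none of these four values, and the Background notes that NG tubes too can be hard to insert, so the sign is open. For the three complications boxed only in Part 3, the gate can lose only records of PEG harm.

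**Size (illustration only).** Let c0 be the complication rate in PEG-fed patients. The share of PEG complications losing prompted capture is f·c ÷ [(1 − f)·c0 + f·c]. The values of f, c and c0 are assumptions; only the 500 comes from the protocol.
- f = 1%, c = 10%, c0 = 3%: lost 500 × 0.01 × 0.10 = 0.5; prompted 500 × 0.99 × 0.03 = 14.85; share 0.5 ÷ 15.35 = 3.3%.
- f = 3%, c = 30%, c0 = 3%: lost 4.5; prompted 14.55; share 4.5 ÷ 19.05 = 23.6%.
- f = 10%, c = 30%, c0 = 3%: lost 15; prompted 13.5; share 15 ÷ 28.5 = 52.6%.
- f = 10%, c = 50%, c0 = 5%: lost 25; prompted 22.5; share 25 ÷ 47.5 = 52.6%.

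The range is about 0.5 to 25 events among 500 patients. Each figure counts events that lose the prompt. They are missing altogether only if no other route picks them up.

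**The case against.** The strongest reply is that nothing is made unreportable. The Adverse Event Card exists for serious procedural events and does not ask whether feed was given. Part 5 is completed for everyone and has room for peritonitis, bleeding and other complications. A patient allocated PEG but never fed by it triggers the request for reasons on the routing page, which is the natural place to record a failed insertion. The worst events therefore have the most alternative routes. The gate is identical for NG, only one secondary outcome is touched, and no rate of attempted but unused tubes is given.

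Most of this stands, and it limits the point. It does not remove it. The free-text line asks why the allocation was not followed, not what complications occurred. Part 5 does not name failed insertion, peritonitis or PEG-site bleeding. The card is confined to major events, a term the protocol does not define. Lesser events in unfed patients depend on someone choosing to write them down, whereas in fed patients they are asked about.

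A reader might infer more than the documents support:
- *That the safety comparison is biased in favour of PEG.* The NG gate loses failed NG insertions too, and no rates are given, so the net direction is not shown.
- *That procedure-related deaths are hidden.* The Background's risk of about 1% would mean about 5 deaths in 500 PEG patients (500 × 0.01). In-hospital deaths are recorded in Part 5 whatever was fed, and the date of any death is sought from the family doctor before six-month follow-up.
- *That intention-to-treat is breached.* The Analyses section fixes analysis by allocation. The routing affects what is recorded, not who is analysed.

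**Conclusion.** The point holds as a weakness in data capture. Prompted recording of procedural complications depends on feed having been delivered, so adverse effects are ascertained unevenly between fed and unfed patients. Procedural harm may be under-recorded, most plausibly for lesser events and for the PEG-specific complications boxed only in Part 3. This rests on sites following the routing as written. The number of events lost is unknown; the illustrative 0.5 to 25 in 500 depends wholly on assumed rates and on no other route recording the event. The net effect on PEG versus NG cannot be established from the protocol. Deaths, the primary outcome (Modified Rankin below 4 in Trial 3), the sample size and the intention-to-treat population are untouched. It is a modest defect in a named secondary outcome, worth correcting because the repair is cheap.

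**What to change.** In the routing table, change the two triggers to *Any feeding via, or any attempt to insert, an NG tube* and *Any feeding via, or any attempt to insert, another type of tube (e.g. PEG)*. Change the headings of Parts 2 and 3 to match. Add three items to each part: was insertion attempted, did it succeed, and was any feed delivered. Compare adverse effects by allocated arm, using these parts together with Part 5 and the Adverse Event Card.

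The change is to form wording only and needs no extra visits, staff or procedures. The downside is a few more part-completed sections, since patients with an attempt but no feed will leave the feed-related items blank.

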## PART 1 Parenteral Fluids Given SINCE Randomisation (Please enter 99/99/99 or 99 if unknown)

Route: (please tick (✓) one box)

Intravenous       Subcutaneous       Both

Date first parenteral fluids given after randomisation: day   month   year

Date last parenteral fluids given: day   month   year

Were fluids given between these dates?  Continuously       Intermittently

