## ***Hospital Discharge Form***

---

At discharge, transfer from the randomising centre or death, the randomising clinician, or the trial support staff in that centre will review the case notes and drug charts, complete a Hospital Discharge Form (Appendix C) and return it to the FOOD Trial Co-ordinating Centre in Edinburgh.

Clinicians who routinely transfer their patients with stroke to another ward/unit/hospital very soon after admission will need to reach an agreement with that ward/unit/hospital such that the allocated feeding regimen will be continued and that the Hospital Discharge Form will be completed on discharge, death or transfer from that ward/unit/hospital.

The data collected will be used to:

- Determine what nutritional support the patient actually received during hospital admission.
- Provide contact data to allow six month follow-up to be organised centrally.
- Provide data concerning early outcome and use of hospital facilities.
- Provide data relating to any adverse events and complications of the feeding regime.

These data should be available from the medical or nursing notes.

If a Hospital Discharge Form has not been received by the Food Trial Co-ordinating Centre before the six months follow-up is due, the FOOD Trial Co-ordinating Centre in Edinburgh will contact the randomising clinician to confirm the patient's whereabouts. If the patient is still in hospital, a hospital version of the Follow-up Form (Appendix E) will be sent to the clinician for completion. The Hospital Discharge Form should then be completed on eventual discharge, transfer from the randomising centre or death.

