## PART 5 This section should be completed for all patients (Please enter 99/99/99 or 99 if unknown)

SINCE this patient was first randomised have they experienced any of the following: No

- Recurrent stroke If so, first noted since randomisation day   month   year
- Neurological worsening (not clearly due to recurrence) If so, first noted since randomisation day   month   year
- Pneumonia If so, first noted since randomisation day   month   year
- Other infections **1** If so, first noted since randomisation day   month   year
- Please specify: \_\_\_\_\_   For office use

- 2** If so, first noted since randomisation day   month   year
- Please specify: \_\_\_\_\_   For office use

- Pulmonary Embolism If so, first noted since randomisation day   month   year
- Deep vein thrombosis If so, first noted since randomisation day   month   year
- Pressure sores If so, first noted since randomisation day   month   year
- Gastrointestinal haemorrhage If so, first noted since randomisation day   month   year
- Other medical complications **1** If so, first noted since randomisation day   month   year
- Please specify: \_\_\_\_\_   For office use

- 2** If so, first noted since randomisation day   month   year
- Please specify: \_\_\_\_\_   For office use

Did the patient survive to discharge from randomising centre?

YES  NO  If **YES**, go to Part 6

If **NO**, please complete the following

Date of death day   month   year

Primary cause of death (please tick (✓) **one box only**)

- Neurological damage from initial stroke (e.g. coning)  Pneumonia  Pulmonary embolism
- Recurrent stroke  Coronary heart disease
- Other vascular, please specify: \_\_\_\_\_
- Non-vascular, please specify: \_\_\_\_\_

Do you think this patient died due to trial treatment? YES  NO

If **YES**, please specify: \_\_\_\_\_   For office use

Cause of death confirmed by autopsy? YES  NO

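### The discharge form prompts for aspiration only in its tube-feeding sections, so a Trial 2 comparison of aspiration by arm would lean against early tube feeding

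*Protocol*

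**What the plan says.** The Protocol's Secondary Outcomes section lists "Adverse effects of feeding regimes". The section on the Hospital Discharge Form gives one of the form's purposes as "Provide data relating to any adverse events and complications of the feeding regime".

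Appendix C decides by feeding route which parts are completed. For parenteral fluids the instruction is "If YES complete PARTS 1, 5, 6 & 7". For normal hospital diet alone it is "If YES complete PARTS 5, 6 & 7". Parts 2 and 3 are opened only if the patient was tube fed after randomisation.

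The parts differ in what they ask:

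- **Part 1**, "Parenteral Fluids Given SINCE Randomisation", asks for the route, the first and last dates and, under "Were fluids given between these dates", whether fluids were continuous or intermittent. It has no item on difficulties.
- **Parts 2 and 3** each ask "Were any difficulties experienced" and offer aspiration as a tick box, without a date.
- **Part 5** is marked "This section should be completed for all patients". It has dated lines for recurrent stroke, neurological worsening, pneumonia, other infections, pulmonary embolism, deep vein thrombosis, pressure sores, gastrointestinal haemorrhage and free-text complications. Aspiration is not on the list.

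**The concern.** Trial 2 randomises between a tube now and a tube no sooner than a week later, with parenteral hydration meanwhile. Which parts of the form are opened therefore depends on allocation. Nearly every immediate-arm patient should reach an aspiration box, because the tube is to be started within three days. A delay-arm patient reaches one only if the clinician later chooses a tube, and the Background expects many patients to improve enough in that time to avoid or reduce tube feeding.

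Delay-arm patients can still aspirate. They enter Trial 2 because they cannot safely take enough by mouth, and the Trial Design section allows them some oral intake. The Background ties aspiration both to unsafe swallowing and to each type of tube.

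At stake is one item of one secondary outcome. With a printed prompt in one arm and only spontaneous mention in much of the other, equal true rates could look unequal, to the disadvantage of early tube feeding. No later analysis can recover an event that the form did not ask about.

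**Working it through.** **The plan's own figure.** The Trial 2 sample size supplies the 1000 per arm used below. For 30% against 36%, two-sided 5% and 80% power:

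n per arm = [1.96 × √(2 × 0.33 × 0.67) + 0.8416 × √(0.30 × 0.70 + 0.36 × 0.64)]² / 0.06² = (1.3034 + 0.5585)² / 0.0036 ≈ 963

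That is 1926 in total. The planned 2000 give 81.5% power, so the stated figure reproduces. The point does not rest on it.

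**Who is asked about aspiration in Trial 2.**

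| Patient | Parts opened | Aspiration prompt |
|---|---|---|
| Immediate arm, tube fed | 2 or 3, plus 5 to 7 | Yes |
| Delay arm, later tube fed | 1, 2 or 3, plus 5 to 7 | Yes |
| Delay arm, never tube fed | 1, plus 5 to 7 | No |

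The third row has no counterpart in the immediate arm, apart from patients who did not receive their allocated tube.

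**Illustration of size.** The Protocol gives neither an aspiration risk nor the share of delay-arm patients later tube fed. Every input here except the 1000 per arm is an assumption:

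- true risk p = 10% in both arms;
- all immediate-arm patients tube fed;
- a share t of the delay arm later tube fed, with the same risk whether tubed or not;
- no capture outside the tick box.

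The ticked rate is then p in the immediate arm and p × t in the delay arm, so the apparent risk ratio is 1/t. With SE = √[(r₁(1 − r₁) + r₂(1 − r₂)) / 1000] and z = (r₁ − r₂) / SE:

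| t | Ticked rates | Risk ratio | z | Chance of p < 0.05 |
|---|---|---|---|---|
| 0.3 | 10% v 3% | 3.3 | 0.07 / 0.0109 = 6.4 | about 100% |
| 0.5 | 10% v 5% | 2.0 | 0.05 / 0.0117 = 4.3 | 99% |
| 0.7 | 10% v 7% | 1.4 | 0.03 / 0.0125 = 2.4 | 67% |
| 0.9 | 10% v 9% | 1.1 | 0.01 / 0.0131 = 0.8 | 12% |

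With equal true rates and equal recording, the last column would be 5%. At a true risk of 5% it reads 99%, 84%, 38% and 8%. At 10% with only 95% of the immediate arm tube fed, it reads about 100%, 97%, 53% and 6%.

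**Effect of other capture.** If a fraction c of aspirations in untubed patients is picked up elsewhere, the delay-arm rate becomes p × [t + (1 − t) × c]. With t = 0.5 and c = 0.4 the bracket is 0.5 + 0.5 × 0.4 = 0.7, which moves the result from the second row to the third. With c = 1 the gap closes.

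**The case against.** The form does have common capture. Everyone is routed to Part 5, which records pneumonia, the main clinical consequence of aspiration, identically in all patients. Part 5 also has two free-text lines for other medical complications, and it records the cause of death. The Adverse Event Card covers any randomised patient. This stands, and it limits the point to aspiration itself. It does not remove the point: free text is unprompted and is completed by centre staff who can know the allocation, and the card is for major events, especially those tied to the feeding policy.

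Most of the boxes in Parts 2 and 3 belong to a tube by nature, such as insertion problems, nasal ulceration, wound infection or bleeding at the gastrostomy site. Their absence for untubed patients is not under-recording. This also stands. In Trial 3 both arms are tube fed, so both are prompted.

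The Protocol does not say that Trial 2 arms will be compared on these boxes, and the choice of items may be made in a statistical analysis plan that is not at hand. So the bias is conditional on that comparison being made. What the form collects, however, is fixed in the Protocol.

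A reader might go further in two directions that the documents do not support:

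- **Trial 1 and the supplement section.** Part 4 asks about difficulties but has no aspiration box, and no effect on a Trial 1 result is shown.
- **Early stopping.** It is tempting to set the z values beside the three-standard-deviation view reported under Data Monitoring Committee. That view concerns a major outcome event at an interim look, and nothing makes this tick box such an event. The z values also use the full sample and assumed inputs.

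**Conclusion.** The gap is real and narrow. Aspiration is prompted where a tube was used and nowhere else, and in Trial 2 tube use follows allocation. A comparison of Trial 2 arms on aspiration would count it more completely in the immediate arm and so lean against early tube feeding.

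The size cannot be fixed from the Protocol. Under the assumptions above, the spurious difference runs from 7 percentage points when 30% of the delay arm is later tube fed to 1 point when 90% is. Any capture through free text or the Adverse Event Card reduces it. It would also be smaller if delay-arm patients who never need a tube have a lower true risk, as those whose swallowing recovers may.

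It does not follow that the whole Trial 2 comparison of adverse effects is biased. Pneumonia, the other Part 5 items, deaths and the primary outcome are recorded without regard to feeding route. This is an inexpensive improvement to one secondary outcome and does not threaten the trial's main conclusions.

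**What to change.** Add a dated aspiration line to Part 5 of the Hospital Discharge Form, in the same layout as the pneumonia line, so that it is asked of every patient whatever the feeding route.

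State, in the Protocol or the statistical analysis plan, that comparisons of adverse effects between Trial 2 arms use Part 5 items, and that the difficulties ticked in Parts 2 and 3 are reported descriptively in that trial.

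The cost is one more line on an existing form and one sentence of text. The form is already completed from the case notes, so no new visit or procedure is needed. A difficulties block in Part 1 is not needed for this purpose.
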